According to Mitchell et al “There are two main disadvantages to CBT-I. First, during the first few weeks of treatment there is often an acute reduction in total sleep time that can lead to the side effect of increased daytime sleepiness which, for some, is enough to lead them to drop out of treatment. Second, improvements from CBT-I are typically not seen until 3-4 weeks into treatment” (p. 3 of 18). Also noteworthy is the emotional response of patients upon learning their sleep will be restricted, commonly with a markedly later bedtime during the implementation of sleep restriction. Although apparently no research to date has assessed patient satisfaction and/or distress during treatment implementation, this may be a factor related to dropout rate with CBT-I. Among ten randomized controlled trials of CBT-I for primary insomnia reporting dropout rate and involving sleep restriction, dropout rates ranged from 0% to 33%. Specifically, 4 studies reported 0% dropout; 1 study reported 7% dropout; 2 studies reported 8% dropout; and dropout rates of 11%, 18% and 33% were each reported in one study (Table 1, Okajima, Komada & Inoue, 2011). In addition, while 36% remission of insomnia disorder is better than 16.9% (comparison group), this means 64% of those completing CBT-I continued to meet diagnostic criteria for Insomnia Disorder (Wu, Appleman, Salazar and Ong, 2015). With all due respect for the major contribution of CBT-I in assisting those with insomnia, there is room for improvement as evidenced by 64% still having Insomnia Disorder upon completion of treatment.

Another potential limitation of CBT-I relates to the mechanism of change and may lead to a means to improve upon the efficacy of behavioral treatment(s) for insomnia. “Research by [name]. and colleagues has established that insomniacs have faster brain wave patterns in bed than good sleepers which is consonant with heightened mental activity.” (Jacobs, 2000, p. 22). The faster brain wave pattern is only partially addressed in CBT-I which focuses on negative sleep talk. However, the emphasis in CBT-I is upon reality testing and/or challenging negative sleep talk, not upon slowing the faster brain wave pattern itself. A behavioral treatment approach which targets the actual here-and-now brain wave frequency

with the goal of slowing the brain wave frequency in the moment at the time when the person wants to go to sleep may further improve their ability to do so.

BRAIN WAVE FREQUENCY AND SLEEP:

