If ANOVA indicates a significant overall difference, pairwise t-tests will test the following hypotheses:

Hypothesis 14a. There will be no statistically significant 12 month follow up minus post-treatment mean differences across the four treatment groups in self report of extent of satisfaction or dissatisfaction with ability to get to sleep at bedtime;

Hypothesis 14b. There will be no statistically significant 12 month follow up minus post-treatment mean differences across the four treatment groups in self report of extent of satisfaction or dissatisfaction with frequency of awakenings after having initiated sleep;

Hypothesis 14c. There will be no statistically significant 12 month follow up minus post-treatment mean differences across the four treatment groups in self report of extent of satisfaction or dissatisfaction with ability to return to sleep after awakenings during the night;

Hypothesis 14d. There will be no statistically significant 12 month follow up minus post-treatment mean differences across the four treatment groups in self report of extent of satisfaction or dissatisfaction with average quantity of sleep;

Hypothesis 14e. There will be no statistically significant 12 month follow up minus post-treatment mean differences across the four treatment groups in self report of extent of satisfaction or dissatisfaction with overall quality of sleep.

Hypothesis 15: Satisfaction with Treatment

There will be no statistically significant differences across treatment types in post-treatment reported overall level of satisfaction with the treatment received as measured with a 5-point Likert Scale on the FEEDBACK QUESTIONNAIRE.

Hypothesis 16: Likelihood to Recommend to Others

There will be no statistically significant differences across treatment types in post-treatment reported level of likelihood to recommend to others the treatment received as measured with a 5-point Likert Scale on the FEEDBACK QUESTIONNAIRE.

MISSING DATA

All data measures will be reviewed upon receipt to ensure no data is missing. Subjects who have not completed the data measures and/or specific items will be asked to do so immediately upon the review having identified missing data. In any situations in which important missing data cannot be gathered, the subject will be eliminated from the study. It is anticipated that in effect 5-10% of subjects will not

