complete 12 month follow-up. These subjects will then be eliminated as relates to analyses involving 12 month follow-up data. Statistical analyses will be conducted to determine whether those with missing data differ significantly from those without missing data using t test comparing the two groups on total scores on Insomnia Severity Index at pre-treatment as well as post-treatment.

STATISTICS

Repeated measures analysis of variance (2 X 4 ANOVA) will be used to test the Hypotheses 1-3, 5-10 and 11-16. Any statistically significant ANOVAs will be followed by pairwise t-test comparisons to identify between group differences. Chi square will be used to test Hypotheses 4 and 11.

SAFETY ANALYSIS

In general the potential risks for participants are minimal. The treatment approaches involved in related studies have been shown to be a safe procedure and in most of the published studies people who underwent these procedures did not report any harmful effects.

Prospective participants will be informed that it is nonetheless possible you may experience some discomforts during the treatment. These may include temporary decrease in time asleep and accompanying daytime drowsiness. Some people may become anxious while initially following the treatment procedures, with increased worry about their sleep difficulty. Anxiety and worry about sleep difficulty are in fact common among persons with insomnia. Therefore identifying and addressing these possibilities will be directly addressed during the treatment, and participants will be given guidance about what to expect and how to manage should these discomforts occur. Prospective participants will also be informed that persons with certain medical illnesses, certain psychiatric illnesses or other sleep disorders may be at increased potential risk of exacerbation of that illness. This is a possibility for participants with epilepsy, bipolar depression, parasomnia, obstructive sleep apnea or other illnesses which have excessive daytime sleepiness as a feature of the parent disorder. The participant may (or may not) be assigned to a treatment which involves sleep restriction. Sleep loss through sleep restriction may

- 1) Lower the threshold for seizures in persons with epilepsy;
- 2) Precipitate mania in bipolar participants;
- 3) Exacerbate parasomnias;
- 4) Prevent adequate ventilation in patients with obstructive sleep apnea; and/or

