9.6 STATISTICAL METHODS AND DETERMINATION OF SAMPLE SIZE

9.7.1 SAMPLE SIZE

It is estimated that 320 prospects will need to be screened in order to have 40 per group for a total of 160 participants.

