9.7.2 ANALYSIS POPULATIONS

1. **Safety Population:** will include all randomized subjects who meet eligibility criteria and meet with their treatment provider for session 1.

2. **Intent-to-Treat Population:** will include all subjects who meet with their treatment provider for session 1 and for whom the treatment provider determines the subject meets diagnostic criteria for 780.52 Insomnia Disorder.
3. **Pre-Protocol (PP) Population:** will include all subjects who complete the 6 sessions of treatment as well as the 3 month, 6 month and 12 month follow up assessment. It is estimated that 80% of those who complete session 1 will complete session 6. It is estimated that 80% of those who complete session 6 will complete the 3 month, 6 month and 12 month follow up assessments. This will result in 25 participants who will have completed the entire study.

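### The one stated check on missing data pools the four arms, so it does not address loss that differs by arm, and it has low power

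*Protocol*

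**What the plan says.** Section 8.0, Missing Data, sets a complete-case rule in two parts. For data that cannot be recovered: "In any situations in which important missing data cannot be gathered, the subject will be eliminated from the study". For the 5-10% expected not to complete month 12: "These subjects will then be eliminated as relates to analyses involving 12 month follow-up data". It then states one diagnostic, a significance test between subjects with and without missing data, "using t test comparing the two groups on total scores on Insomnia Severity Index at pre-treatment as well as post-treatment". Treatment arm does not appear in it.

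Other parts of the protocol that bear on the check:

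- Hypotheses 1 to 16 (Section 8.0) all compare the four treatment groups.
- The Introduction, under the limitations of CBT-I, cites a review which says that the early loss of sleep time brings "increased daytime sleepiness which, for some, is enough to lead them to drop out of treatment". The protocol adds that distress at sleep restriction may play a part in CBT-I dropout.
- Section 9.7.1 plans screening "in order to have 40 per group for a total of 160 participants". Section 9.7.2 gives the retention assumption: "It is estimated that 80% of those who complete session 1 will complete session 6". It then assumes a further 80% from session 6 through the follow-up assessments.
- Section 9.3.3 asks all randomized early discontinuers to attend an Early Termination (ET) visit with the Visit 8 evaluations, and has the reason for discontinuation recorded. Section 9.5.3.8 includes the ISI at Visit 8.

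**The concern.** A comparison between arms among those who remain is biased by the difference between arms in (proportion lost) x (outcome gap between lost and retained). The planned test estimates a different quantity, the average gap over all four arms. Gaps in opposite directions offset each other in that average, and a gap confined to some arms is diluted. The test also says nothing about whether loss rates differ by arm.

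This matters because the protocol gives reasons to suspect arm-specific loss: sleep restriction in the CBT-I arms, and, in Sections 9.3.3 and 9.4.10, discontinuation for lack of efficacy or worsening sleep, which could fall more heavily on less effective arms. With subjects removed from the analysis, this test is the only stated means of judging whether the remaining subjects give a fair comparison.

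**Working it through.** **Inputs.** 160 subjects, 40 per arm (Section 9.7.1). Two successive 80% retention rates (Section 9.7.2). 5-10% not completing month 12 (Section 8.0). Assumptions: all 160 complete session 1; two-sided alpha 0.05; gaps in SD units.

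**The plan's own figure.** 40 x 0.80 x 0.80 = 25.6, which matches the stated 25 completers if read per group. Overall, 160 x 0.64 = 102. Loss before session 6 is 160 x 0.20 = 32. Loss after it is 128 x 0.20 = 25.6, about 26. (Section 9.7.2 thus implies 36% overall loss by month 12 against the 5-10% in Section 8.0. That is a separate inconsistency, and both rates are carried below.)

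**Power of the pooled test.** The difference detectable with 80% power is about (1.96 + 0.84) x sqrt(1/n1 + 1/n2), slightly larger with the t distribution.

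| Loss assumed | Lost v retained | Result |
|---|---|---|
| Section 9.7.2, before session 6 (pre-treatment ISI) | 32 v 128 | 80% power for 0.56 SD |
| Section 9.7.2, after session 6 (post-treatment ISI) | 26 v 102 | 80% power for 0.62 SD |
| Section 8.0, 5% | 8 v 152 | about 28% power for 0.5 SD |
| Section 8.0, 10% | 16 v 144 | about 48% power for 0.5 SD |

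**What pooling hides.** Let a share p be lost in every arm. An arm's complete-case mean is off by p x gap. For a CBT-I arm against Sleep Hygiene:

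| Assumed pattern | Average gap in pooled test | Bias, p = 0.20 | Bias, p = 0.05 to 0.10 |
|---|---|---|---|
| Lost are 0.5 SD worse in the two CBT-I arms, 0.5 SD better in the other two | 0 | 0.20 x 0.5 x 2 = 0.2 SD | 0.05 to 0.10 SD |
| Lost are 0.5 SD worse in the two CBT-I arms, no gap in the other two | (0.5 + 0) / 2 = 0.25 SD | 0.20 x 0.5 = 0.1 SD | 0.025 to 0.05 SD |

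In the second pattern the pooled test has something to find, but 0.25 SD is far below the 0.56 to 0.62 SD it can detect with 80% power.

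**Simulation.** 4,000 trials, 40 per arm, assumed ISI SD 4 and pre-post correlation 0.5. The post-treatment test was run as if every subject had that score.

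- Loss of 10/30/30/10% by arm, at random: the pooled t test rejects in 4.7% (pre-treatment) and 8.4% (post-treatment) of trials; a chi-square test of missingness by arm rejects in 77.5%. The arm contrast is essentially unbiased here, because unequal rates alone do no harm.
- About equal rates, with two arms losing poor responders and two losing good ones: the pooled test rejects in 5.6% and 4.2%, while the contrast between two arms is off by about 1.7 ISI points. The chi-square test also misses this (4.9%).

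The second case assumes stronger selection than the tables. It shows that counts by arm are not enough and that scores must be compared within arm as well.

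**The case against.** Several stronger readings are tempting, and the documents do not support them.

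- *Dropouts have no post-treatment ISI, so half the check cannot be done.* Subjects lost after the end of treatment have the Visit 8 ISI, and these are the month-12 non-completers named just before the check. Those who leave during treatment are asked for the same evaluations at the ET visit, with a written request if they do not return. The score is lacking only for those who leave during treatment and skip that visit.
- *The protocol expects the relation between dropout and outcome to differ by arm.* It does not. The Introduction reviews literature and raises a possible link between CBT-I and the dropout rate. Section 9.7.2 assumes one retention rate for all arms.
- *The biases cancel, so the test cannot detect anything.* Exact cancellation is a constructed case. Nothing in the protocol says that the FOA or Sleep Hygiene arms lose better responders. In the one-sided case the pooled gap is not zero, only small relative to the test's power.
- *A non-significant result will be taken as validation.* The protocol attaches no decision rule to the test. A reader could take it that way, but the text does not say so.

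Two further objections have force. The bias comes from eliminating subjects, so changing the check alone leaves the main comparisons as they are. An analysis plan that is not shown may also add to the check. Both limit the weight of the point. They do not remove it, because the protocol itself names the test and fixes it in a form that does not address the four-arm question.

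**Conclusion.** The point holds in limited form. The only check stated for the complete-case analyses is pooled over arms, does not examine loss by arm in rate or in relation to outcome, and has low power. It is worth correcting, but it is not evidence that the trial's comparisons will be biased.

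The illustrative bias runs from 0.025 SD (only the CBT-I arms losing worse responders, 5% loss) to 0.2 SD (opposite selection, 20% loss). These sizes rest on an assumed 0.5 SD gap and equal loss in all arms. The power figures rest only on the protocol's numbers and a two-sided 0.05 level.

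**What to change.** In Section 8.0, Missing Data, replace the pooled significance test with:

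1. Counts of missingness by arm and recorded reason, at post-treatment and at month 12.
2. Within each arm, pre-treatment ISI, and post-treatment or ET ISI where available, for subjects with against without missing data. Report differences with confidence intervals, not as a pass/fail test.
3. A sensitivity analysis of the ISI comparisons in which missing values are shifted by a delta that may differ by arm, over a range set in advance.

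Do not use a logistic model of missingness on arm, two ISI scores and all their arm interactions. It needs 3 + 2 + 6 = 11 slopes for some 8 to 32 events, which is too few.

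The data are already collected: the reason for discontinuation, and ISI at screening and at Visit 8 or ET. The cost is revised wording and a little programming. The downside is imprecision. With 8 lost and 32 retained in an arm, the 95% interval for the gap is about +/- 1.96 x sqrt(1/8 + 1/32) = 0.77 SD, and it is wider at 5-10% loss. This is why the delta-adjusted analysis is needed alongside the descriptive comparison.

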Hypothesis 3: Treatment Effect on Insomnia Severity

There will be no statistically significant post-treatment minus pre-treatment mean differences across the four treatment groups in insomnia severity as measured by the Insomnia Severity Index (ISI).

Hypothesis 4: Treatment Effect on Insomnia Diagnosis

There will be no statistically significant (chi square) post-treatment minus pre-treatment mean differences across the four treatment groups in the percentage of subjects who meet DSM-5 criteria for 780.52 Insomnia Disorder across time (pre-treatment; post-treatment).

Hypothesis 5: Treatment Effect on Self Report Sleep Satisfaction Measures

There will be no statistically significant overall post-treatment minus pre-treatment differences across the four treatment groups in overall satisfaction/dissatisfaction with sleep using standardized sum scores for data from subjects across the five likert scale measures of satisfaction/dissatisfaction on the Self Report Sleep Measures.

If ANOVA indicates a significant overall difference, pairwise t-tests will test the following hypotheses:

Hypothesis 5a. There will be no statistically significant post-treatment minus pre-treatment mean differences across the four treatment groups in self report of extent of satisfaction or dissatisfaction with ability to get to sleep at bedtime;

Hypothesis 5b. There will be no statistically significant post-treatment minus pre-treatment mean differences across the four treatment groups in self report of extent of satisfaction or dissatisfaction with frequency of awakenings after having initiated sleep;

Hypothesis 5c. There will be no statistically significant post-treatment minus pre-treatment mean differences across the four treatment groups in self report of extent of satisfaction or dissatisfaction with ability to return to sleep after awakenings during the night;

Hypothesis 5d. There will be no statistically significant post-treatment minus pre-treatment mean differences across the four treatment groups in self report of extent of satisfaction or dissatisfaction with average quantity of sleep;

Hypothesis 5e. There will be no statistically significant post-treatment minus pre-treatment mean differences across the four treatment groups in self report of extent of satisfaction or dissatisfaction with overall quality of sleep.

Hypothesis 6: Treatment Effect on Subjective Sleep Distress

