A schematic of the study design is presented in [Figure9.1-1](#). The Schedule of Evaluations is presented in Section [2.0](#). Detailed descriptions of each study visit can be found in Section [9.5.6](#).

FIDURE 9.1-1

STUDY DESIGN

9.2

DISCUSSION OF STUDY DESIGN

This is a randomized, open label, sleep hygiene, controlled, 6-week study to compare the efficacy of four (CBT-I, FOA, Combined CBT-I and FOA and Sleep Hygiene) different behavioral approaches for the treatment of adult subjects with insomnia. In this study, investigators will enroll patients, male and female, who are 18 or older to 72 years. Insomnia Severity Index > or = 10 and meet diagnostic criteria for Insomnia Disorder per DSM-5 willing and able to sign Informed consent form not planning on moving away from the area for the subsequent 12 weeks. In this study, safety and efficacy assessments are included during every visit to determine adequacy of response, safety, and tolerability.

9.3

SELECTION OF STUDY POPULATIONS

Inclusion/Exclusion criteria to be assessed at Screening (Visit 1) and Every Visit (Visit 2, 3, 4, 5, 6, 7, 8, 9, 10 and 11)

9.3.1

INCLUSION CRITERIA

All potential participants must meet these inclusion criteria:

1. Both genders
2. Age \geq 18 to 72 years
3. Insomnia Severity Index > or = 10
4. Meet diagnostic criteria for Insomnia Disorder per DSM-5
5. Be willing and able to sign Informed consent form
6. Not planning on moving away from the area for the subsequent 12 weeks.

9.3.2

EXCLUSION CRITERIA

Participants who answer “yes” to any of the following will be excluded:

1. Females who are lactating or who are pregnant
2. Night shift workers, and individuals who nap 3 or more times per week over the preceding month
3. Consumption of caffeine beverages (i.e. tea, coffee, or cola) comprising usually more than 5 cups or glasses per day
4. Participation in another trial for insomnia
5. Persons unable to complete the study questionnaires and psychological tests
6. Persons who are unable to participate for the entire duration of the study, or in the opinion of the investigators, are likely to be non-compliant with the obligations inherent in the trial participation
7. Persons self-describing with severe anxiety or severe depression
 - a. (BDI score of 29 or higher) or severe anxiety (BAI score of 36 or higher).
8. Persons with a history of epilepsy, seizures, or dementia

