9.5.3.1 Visit 1 (Screening)

At Screening (Visit 1), study procedures will be reviewed with the patient, and documentation of informed consent will be obtained ([Section 5.3](#)). After informed consent is obtained, patients will be assigned a unique "Participant Number" (PN) ([Section 5.0](#)). A review of inclusion/exclusion criteria and other screening assessments will be conducted to determine the patient's eligibility for enrollment ([Sections 9.3.1](#) and [9.3.2](#)).

At Screening (Visit 1), the following procedures will also be performed:

1. Obtain and record medical (surgical, neurological), psychiatric history
2. Obtain and record prior medication history, nondrug psychiatric treatment history, and current medication status
3. Review of all inclusion/exclusion criteria
4. Administer ISI (Insomnia Severity Index)
5. Administer BAI (Beck Anxiety Inventory)
6. Administer BDI (Beck Depression Inventory)
7. Administer SRSM (Self Report Sleep Measures)
8. Administer WSL (Weekly Sleep Log)

9. Administer CGI-S (Clinical Global Impression –Severity Scale)
10. Administer CGI (Clinical Global Impression)
11. Administer Q-LES (Quality of Life Enjoyment and Satisfaction)
12. Administer C-SSRS (Columbia-*Suicide* Severity Rating Scale)
13. Review concomitant medications

Schedule Visit 2 up to 14 days after Visit 1

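### The 2 x 4 repeated-measures ANOVA is a change-score test. For H1, H3, H5-H8 and H10, ANCOVA on the same baseline data would be at least as precise and usually more so.

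*Protocol*

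**What the plan says.** The Statistics paragraph of Section 8.0 states: "Repeated measures analysis of variance (2 X 4 ANOVA) will be used to test the Hypotheses 1-3, 5-10 and 11-16". It continues: "Any statistically significant ANOVAs will be followed by pairwise t-test comparisons to identify between group differences". The Statistical Analysis row of the Synopsis names the same method for H1 to H3. No baseline covariate is mentioned anywhere in the protocol.

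The hypotheses are worded as differences between two times, compared across arms. H3, for example, concerns "post-treatment minus pre-treatment mean differences across the four treatment groups in insomnia severity as measured by the Insomnia Severity Index (ISI". H1 to H3 and H5 to H7 use post-treatment against pre-treatment, and H8 to H10 use 12 months against pre-treatment. H12 to H14 use 12 months against post-treatment. H15 and H16 have a single time point. H15 reads: "There will be no statistically significant differences across treatment types in post-treatment reported overall level of satisfaction with the treatment received".

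The Visit 1 list in Section 9.5.3.1 includes "Administer ISI (Insomnia Severity Index", "Administer SRSM (Self Report Sleep Measures" and "Administer WSL (Weekly Sleep Log". Section 9.5.3.2 places randomisation at the end of Visit 2. The same three instruments return at Visit 8 (Section 9.5.3.8) and Visit 11 (Section 9.5.3.11).

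**The concern.** A change score subtracts the whole baseline value, as though the regression slope of follow-up on baseline were 1. ANCOVA estimates that slope. In a randomised trial both methods target the same between-arm difference, so the choice affects precision. It also affects how a chance baseline imbalance is handled: when the true slope is below 1, the change score over-corrects for it.

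Precision is scarce here. The trial plans 40 per arm, expects attrition, and compares active arms with each other, where differences may be small. Any variance removed by using baseline values already collected would otherwise have to be bought with more participants.

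**Working it through.** **Inputs from the Protocol.** Four arms, 1:1:1:1, 40 per arm (Synopsis; Section 9.7.1). 80% of those completing session 1 complete session 6, and 80% of those complete all follow-ups (Section 9.7.2). Entry requires "Insomnia Severity Index > or = 10" (Section 9.3.1).

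**Inputs assumed, because the Protocol gives none.** Two-sided alpha 0.05; a between-arm difference of 0.5 post-treatment SD; rho 0.3, 0.5 or 0.7; SD_pre/SD_post of 1 or 0.7.

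**1. Numbers per arm.** Session-6 completers: 40 x 0.80 = 32. Full completers: 32 x 0.80 = 25.6, against the stated 25. That figure fits only a per-arm count, since the whole-trial count would be 160 x 0.64 = 102.4. The 40 per arm cannot be reproduced, because no power inputs are given.

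**2. The planned test is a change-score test.** With two time points, the group-by-time F equals the one-way ANOVA F on post minus pre. On one simulated data set of 4 x 40, both gave F = 1.7195.

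**3. Error variances.** Write k = SD_pre/SD_post and set SD_post = 1.
- Change score: k^2 + 1 - 2 x rho x k
- ANCOVA: 1 - rho^2
- Difference: (k - rho)^2, which is never negative and is zero when rho = k

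With k = 1 the ratio of ANCOVA to change variance reduces to (1 + rho)/2.

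| k | rho | Change | ANCOVA | Ratio | Variance saved |
|---|---|---|---|---|---|
| 1 | 0.3 | 1.40 | 0.91 | 0.65 | 35% |
| 1 | 0.5 | 1.00 | 0.75 | 0.75 | 25% |
| 1 | 0.7 | 0.60 | 0.51 | 0.85 | 15% |
| 0.7 | 0.3 | 1.07 | 0.91 | 0.85 | 15% |
| 0.7 | 0.5 | 0.79 | 0.75 | 0.95 | 5% |
| 0.7 | 0.7 | 0.51 | 0.51 | 1.00 | 0% |

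The rows with k = 0.7 matter for the ISI, because the entry cutoff truncates its baseline distribution and may narrow the baseline SD.

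**4. Equivalent sample size, k = 1.** 40 per arm under ANCOVA is worth 40/0.65 = 61.5, 40/0.75 = 53.3 or 40/0.85 = 47.1 per arm under change scores.

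**5. Pairwise power.** Two-sample t-test on 2n - 2 degrees of freedom, noncentrality 0.5/sqrt(2V/n), where V is the error variance from step 3. The table takes k = 1.

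| n per arm | rho 0.3 | rho 0.5 | rho 0.7 |
|---|---|---|---|
| 40 (all randomised) | 46% to 64% | 60% to 72% | 81% to 87% |
| 32 (session-6 completers) | 38% to 54% | 50% to 62% | 72% to 79% |
| 25 (12-month completers) | 31% to 44% | 41% to 52% | 61% to 68% |

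At k = 0.7 and rho 0.5 the gain is small: 70% to 72% at 40 per arm, 60% to 62% at 32, and 50% to 52% at 25.

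**6. Where a usable baseline exists.**
- H3 and H10 (ISI), and H5 to H7 (SRSM): yes, from Visit 1.
- H1 and H8 (sleep log): Sections 9.1.3, 9.4.5 and 9.5.3.1 place the log at intake, but the sleep-log row of the Schedule of Evaluations, as far as the extracted table can be read, has no screening mark.
- H2 and H9 (ActiWatch): the watch goes back at the first session (In Person Screening text, Section 9.1.2), and no visit list schedules it afterwards.
- H12 to H14: the earlier value is post-treatment.
- H15 and H16: no earlier value exists.

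**The case against.** The strongest reply is that nothing here is wrong. The planned test is valid, it matches hypotheses written as differences, and a statistical analysis plan not at hand might add a covariate. The first two parts stand, so this is a matter of efficiency. The third carries less weight: the protocol names the model, its dimensions and the follow-up test, and an analysis plan using ANCOVA would depart from that text.

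The size of the gain is also open to challenge, and this stands as well. The (1 + rho)/2 ratio needs equal SDs, and the saving can vanish.

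A reader might infer more than the documents support:
- *That the planned analysis is biased.* It is not, given randomisation.
- *That ANCOVA is strictly better whenever rho is below 1.* With unequal SDs the saving is zero at rho = SD_pre/SD_post, which can lie well below 1.
- *That the remedy suits every hypothesis in the quoted sentence.* Adjusting the 12-month value for the pre-treatment value under H12 to H14 would replace a question about maintenance with one about total effect. H2, H9, H15 and H16 lack the data.
- *That only about 25 per arm are available for every contrast.* That count is of participants finishing all follow-ups. The post-treatment tests need session-6 completion, about 32 per arm.

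**Conclusion.** The point holds as a loss of precision for H1, H3, H5 to H8 and H10, with H1 and H8 conditional on an intake sleep log. Over the range examined, ANCOVA saves between 0% and 35% of error variance, and it never increases that variance apart from the one degree of freedom spent. The 12-point rise in power at 40 per arm (60% to 72%) rests on rho 0.5, equal SDs and a 0.5 SD difference, all assumed. For the ISI, a narrower baseline SD could reduce the rise to about 2 points or to nothing. The change is worth making, but the validity of the trial does not depend on it.

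**What to change.** Amend the Statistics paragraph of Section 8.0 and the Statistical Analysis row of the Synopsis. For H1, H3, H5 to H7, analyse the post-treatment value, and for H8 and H10 the 12-month value, by ANCOVA with arm as factor and the pre-treatment value of the same measure as covariate. Take the pairwise contrasts from that model in place of separate t-tests. State which visit supplies the pre-treatment SRSM, since it is collected at both Visit 1 and Visit 2.

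Before applying this to H1 and H8, reconcile the Schedule of Evaluations with Sections 9.1.3, 9.4.5 and 9.5.3.1 on the intake sleep log. Leave H2, H9 and H12 to H16 out of the change. While editing, note that the same paragraph assigns H11 to both ANOVA and chi-square and puts the single-time H15 and H16 under a two-time model. Those are separate corrections.

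Cost: a wording change and one degree of freedom per model, with no new data for the ISI and SRSM outcomes.
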